1.2 Objectives

The objectives and related endpoints are listed in [Table 1-1](#).

Table 1-1 Objectives and related endpoints

	Objective	Endpoint
Primary	To demonstrate the antitumor activity of LDK378, as measured by overall response rate (ORR) to LDK378 by investigator assessment per RECIST 1.1.	ORR, defined as the proportion of patients with a best overall confirmed response of CR or PR in the whole body as assessed per RECIST 1.1 by the investigator.
Key secondary	To evaluate disease control rate (DCR).	DCR, calculated as the proportion of patients with best overall response of CR, PR, or SD.
	To evaluate time to tumor response (TTR).	TTR, calculated as the time from first dose of LDK378 to first documented response (CR or PR) for patients with confirmed CR or PR.
	To evaluate duration of response (DOR).	DOR, calculated as the time from the date of the first documented response (CR or PR) to the first documented disease progression or death due to any cause for patients with confirmed CR or PR.

	Objective	Endpoint
Other secondary	To evaluate progression free survival (PFS).	PFS, calculated as the time from first dose of LDK378 to date of first documented disease progression (per RECIST 1.1) or date of death due to any cause.
	To evaluate overall survival (OS).	OS, calculated as the time from first dose of LDK378 to death from any cause.
	To evaluate overall intracranial response rate (OIRR).	OIRR, calculated as the proportion of patients with a best overall confirmed response of CR or PR in the brain assessments for patients having measurable brain metastases at baseline.
	To evaluate the safety profile.	AEs, ECGs and laboratory abnormalities.

All tumor-response related endpoints will be evaluated using tumor responses assessed by investigator according to RECIST 1.1.

2 Statistical methods

This section and its subsections will be imported to Section 9.7 of the Clinical Study Report (CSR) after the analyses have been conducted. This section of the RAP follows the CSR template structure of Section 9.7 as of the release date of this document.

The text will be changed to the past tense when imported into the CSR; references to Section 4 of the RAP, where additional details are provided for programming implementation, may be removed in the CSR.

In what follows, study drug refers to LDK378.

2.1 Data analysis

Data will be analyzed by Novartis Oncology Biostatistics and Statistical Programming personnel according to the data analysis section 10 of the CLDK378A1201 protocol, which will be available in Appendix 16.1.1 of the CSR. Important information is given in the following sections and details are provided, as applicable, in Section 4 from which Appendix 16.1.9 of the CSR will be extracted.

SAS® version 9.4 (or later version if available at time of database lock) will be used in all analyses.

Data from all patients who signed informed consent in centers that participate in this study will be combined and used in the analysis. Data collected after withdrawal of informed consent will not be reported. Due to expected small size of enrollment at individual centers, no center effect will be assessed. Each analysis will use all data in the database up to the analysis cut-off date, determined prior to database lock.

The analysis cut-off date for the primary analysis of study data will be around 168 days after the first dose of study drug for the last patient enrolled corresponding to when all patients have either completed at least 6 cycles of treatment, i.e., 168 days (1 cycle = 28 days), or discontinued earlier. The results from primary analysis will be reported in the primary (interim) CSR. Following the primary analysis time point, the study will remain open. Patients still being followed on the study will continue as per the schedule of assessments. The analysis cut-off date for the final analysis of study data will be established at the end of the study when at least 75% of deaths have occurred. The results from final analysis will be reported in the final CSR. Note that the analysis cut-off date and reporting strategy may be changed according to the development and/or NDA submission status of LDK378.

[Section 4.1](#) provides further details regarding data to be included in the analyses.

General presentation of descriptive summaries

Qualitative data (e.g., gender, race) will be summarized by frequency counts and percentages. Percentages will be calculated using the number of patients in the relevant population or subgroup as the denominator.

Continuous data (e.g., age, body weight) will be summarized by appropriate descriptive statistics (i.e., mean, standard deviation, median, minimum, and maximum).

Subgroup analysis

Key efficacy endpoints (best overall response, ORR, and DCR) will be summarized for the following subgroups:

- Brain metastases at baseline: (presence, absence)
Note: for the subgrouping the brain metastases are defined as measurable or non-measurable disease in the brain at baseline. List of lesion locations considered to be brain metastases is provided in [Section 4.7.3](#).
- Prior ALK inhibitor: (alectinib only, alectinib and crizotinib)
- Best response to prior alectinib: (CR/PR, SD/PD/UNK)

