4.3 Definition of end of the study

There will be no interim analysis of efficacy. The primary analysis will occur once all patients have completed at least 6 cycles of treatment with LDK378 or have discontinued earlier. Following the primary analysis time point, the study will remain open. Patients still being followed on the study will continue as per the schedule of assessments.

The study will end once at least approximately 75% of patients have died or are lost to follow-up. The final analysis of study data will be conducted at the end of the study. All available data from all patients up to this cutoff date will be analyzed. These data will be summarized in the Clinical Study Report (CSR).

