6.1.4 Definition of treatment cycle

A treatment cycle is defined as 28 calendar days from the start of treatment with LDK378 (Day 1, Cycle 1) for the purposes of scheduling procedures and evaluations.

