7.1 Study flow and visit schedule

Table 7-1 lists all of the assessments and indicates with an “X” the visits when they are performed. Each treatment cycle is 28 days (the 28 days cycle length is fixed regardless of whether the dose of LDK378 is withheld). All visits are to be scheduled according to the appropriate number of calendar days from Cycle 1 Day 1 of study drug administration. A visit window of +/- 1 day in Cycle 1 and +/- 3 days in Cycle 2 onwards is allowed. Imaging evaluations may be performed +/-7 days of the due date of the assessment.

Note: If treatment with LDK378 is withheld at any time during the study, all study visits, safety and efficacy assessments should continue according to the appropriate number of calendar days from Cycle 1 Day 1 as per the schedule of assessments.

All data obtained from these assessments must be supported in the patients’ source documentation. No eCRF will be used as a source document. The table indicates which assessments produce data to be entered into the database (D) or remain in the source documents only (S).

Visit name	Category	Protocol Section	Screening Phase	Treatment Phase				Post treatment follow up phase			Survival follow-up phase
				Cycle 1 (28 d)		Subsequent cycles (28 d)	End of study Treatment (EOT)	30-day safety follow-up	Tumor follow- up if no PD at the EOT	Study phase completion	
Screening Visit (Day -28 to Day -1)				Cycle 1 Day 1	Cycle 1 Day 15	Day 1	End of treatment visit				
Antineoplastic therapies since discontinuation of study treatment	D	7.1.5.3.						X	X		X Every 12 weeks
Survival assessment	D	7.1.5.3.									X Every 12 weeks

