7.2.1.2 Subsequent imaging for response assessment

Tumor evaluations as described in [Table 7-2](#) should be performed using the same imaging modality used at baseline, irrespective of study treatment interruption or actual dosing (see [Table 7-1](#)).

Tumor assessment for response determination will be made every 8 weeks starting from Day 1 of Cycle 3 (+/- 7 days window). **The 8 weeks interval should be respected regardless of whether treatment with LDK378 is temporarily withheld.**

Clinical suspicion of disease progression at any time requires a physical examination and radiological confirmation to be performed promptly rather than waiting for the next scheduled radiological assessment.

Each lesion that is measured at baseline must be measured by the same method (either same radiological method or by photography, including a metric ruler) and when possible, the same local radiologist/physician throughout the study so that the comparison is consistent. If an off-schedule imaging assessment is performed because progression is suspected, subsequent imaging assessments should be performed in accordance with the original imaging schedule.

Combined PET/CT may be used only if the CT is of similar diagnostic quality as a CT performed without PET, including the utilization of oral and IV contrast media. At the discretion of the Investigators, FDG-PET scans may be performed to document PD per RECIST 1.1 ([Appendix 2](#)).

Table 7-2 Imaging assessment collection plan

Procedure	Screening/Baseline	During Treatment/Follow-up
CT or MRI (Chest, Abdomen)	Mandated	every 8 weeks
Whole bone scan	Mandated	If clinically indicated
Brain CT or MRI	Mandated	Cycle 3 then every 2 cycle (i.e. every 8 weeks): only if positive at baseline or clinically indicated only if positive at baseline or clinically indicated.

 CT scan or MRI of other metastatic sites (e.g. neck, pelvis, etc) Localized bone CT scan, MRI or x-ray (for any lesions identified on the whole body bone scan that are not visible on the chest/abdomen CT scan or MRI) 	if clinically indicated	Cycle 3 then every 2 cycle (i.e. every 8 weeks): only if positive at baseline or clinically indicated only if positive at baseline or clinically indicated.

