2.6 Treatments (study drug, concomitant therapies, compliance)

The Safety Set will be used for all medication data summaries and listings unless otherwise specified.

Study drug and study treatment

Study drug and study treatment both refer to LDK378 and will be used interchangeably.

Date of first/last administration of study drug

The date of first administration of study drug is defined as the first date when a non-zero dose of study drug was administered and recorded on the [Dosage Administration Record (DAR)] eCRF page. For the sake of simplicity, the date of first administration of study drug will also be referred to as start date of study drug.

The date of last administration of study drug is defined as the last date when a non-zero dose of study drug was administered and recorded on the DAR eCRF page. This date will also be referred to as last date of study drug.

Study day

The study day for all assessments (e.g., tumor assessment, death, disease progression, tumor response, performance status, adverse event onset, laboratory abnormality occurrence, vital sign measurement, and dose interruption) will be calculated using the start date of study drug as the origin. For assessments occurring after or on the start date of study drug, study day will be calculated as:

Study day = Event date – Start date of study drug + 1.

The first day of study drug is therefore study day 1.

For any assessment or events such as baseline disease characteristics or medical history (e.g., time since diagnosis of disease) occurring prior to the start of the study drug, study day will be negative and will be calculated as:

Study day = Event date – Start date of study drug.

The study day will be displayed in the relevant data listings.

Dose exposure and intensity

Definitions of study drug exposure variables, as well as intermediate calculations, are provided in [Table 2-1](#).

Table 2-1 Study drug exposure variables

Variable	Definition
Duration of exposure (days):	Last date of study drug – Start date of study drug + 1 (Periods of interruption are not excluded.)
Cumulative dose (mg):	Total dose of study drug taken by a patient in the study
Number of dosing days (days):	Duration of exposure (days) – Number of zero dose days
% of actual days dosed (%):	$100 \times \text{Number of dosing days} / \text{Duration of exposure (days)}$
% of days received full dose (%):	$100 \times \text{Number of days received full (planned) dose} / \text{Duration of exposure (days)}$

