2.8 Analysis of secondary variables

2.8.1 Efficacy

The key secondary and other secondary efficacy endpoints are provided in [Table 1-1](#). All tumor response related endpoints under the secondary efficacy objectives (DCR, TTR, DOR, PFS, and OIRR), as well as the primary efficacy endpoint ORR, will be analyzed based on the investigator assessments as per RECIST 1.1. Confirmation of response is required for all response endpoints, as per RECIST 1.1.

The definitions and details on the derivation of the efficacy endpoints are given in Section 15 (Appendix 2) of the CLDK378A1201 protocol. Further details and rules needed for programmatic implementation of RECIST 1.1 guidelines are provided in [Section 4.7.1](#).

All secondary efficacy endpoint analyses will be performed based on the FAS, unless otherwise specified. All efficacy data, such as tumor assessments and respective efficacy endpoints, will be listed by patient.

Best overall response and DCR will be summarized by subgroup (as defined in [Section 2.1](#)) as well as the primary efficacy endpoint ORR.

Best overall response

Best overall response (BOR) will be assessed based on reported lesion responses at different evaluation time points. Both CR and PR must be confirmed by repeat assessments performed not less than 4 weeks after the criteria for response are first met. The next scheduled assessment may be used for purposes of confirmation of response. If there is only one confirmatory assessment available which has been performed earlier, the status PR or CR will not be assigned. Unconfirmed PR and unconfirmed CR are considered as SD if >6 weeks after start of study drug, otherwise considered as UNK. BOR for each patient is determined from the sequence of overall (lesion) responses according to the following rules:

- CR = at least two determinations of CR at least 4 weeks apart before progression.
- PR = at least two determinations of PR or better at least 4 weeks apart before progression (and not qualifying for a CR).
- SD = at least one SD assessment (or better) >6 weeks after start of study drug (and not qualifying for CR or PR).
- PD = progression ≤12 weeks after start of study drug (and not qualifying for CR, PR or SD).
- UNK = all other cases (i.e., not qualifying for confirmed CR or PR and without SD after more than 6 weeks or progression within the first 12 weeks)

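### The primary cut-off falls at the midpoint of the last patient's week-24 scan window and is not tied to that scan, so a late-confirmed response could be scored as SD in the primary ORR

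*SAP*

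**What the plan says.** **Cut-off.** SAP 2.1 sets it "around 168 days after the first dose of study drug for the last patient enrolled", and the results go into the primary (interim) CSR. Protocol 4.3 gives the trigger: "The primary analysis will occur once all patients have completed at least 6 cycles of treatment with LDK378 or have discontinued earlier". SAP 2.1 adds: "Note that the analysis cut-off date and reporting strategy may be changed according to the development and/or NDA submission status of LDK378". SAP 4.1 admits only data dated on or before the cut-off.

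**Calendar.** Protocol 6.1.4: "A treatment cycle is defined as 28 calendar days from the start of treatment with LDK378". SAP 2.6: "The first day of study drug is therefore study day 1". Protocol 7.2.1.2 schedules tumor assessments every 8 weeks from Cycle 3 Day 1, and Protocol 7.1 gives the tolerance: "Imaging evaluations may be performed +/-7 days of the due date of the assessment".

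**Response.** ORR counts confirmed responses only. SAP 2.8.1: "Both CR and PR must be confirmed by repeat assessments performed not less than 4 weeks after the criteria for response are first met". The same section lets the next scheduled scan serve as confirmation, and it scores an unconfirmed response more than 6 weeks after start of drug as SD.

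**The concern.** The cut-off follows the count of treatment cycles, while the primary endpoint depends on the scan schedule. For a response first seen at week 16, the scheduled confirming scan is the week-24 one. The same holds when a week-8 PR is followed by an unknown assessment at week 16. If the last patient's week-24 scan is taken in the second half of its allowed window, it falls after the cut-off. A patient who met every protocol requirement is then a non-responder in the primary report, and also drops out of TTR and DOR, which cover confirmed responders only. DCR does not change, because SD still counts.

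Whether the response counts would depend on the day within the permitted window on which the scan was booked. With 20 patients, one responder is 1/20 = 5 percentage points of ORR.

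**Working it through.** **1. Plan's own figures.** With N = 20 and at least 6 responders required (SAP 2.9), the binomial tail P(X ≥ 6) is 58.4%, 75.5% and 87.4% at true ORRs of 30%, 35% and 40%. The Clopper-Pearson 95% CI for 6/20 is 11.9-54.3%. All of these reproduce the SAP.

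**2. Scan days.** Cycle k Day 1 is study day (k − 1) × 28 + 1, ± 7 days.

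| Scan | Due day | Window |
|---|---|---|
| Cycle 3 Day 1 | 57 | 50-64 |
| Cycle 5 Day 1 | 113 | 106-120 |
| Cycle 7 Day 1 | 169 | 162-176 |

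**3. Cut-off day.** First dose is day 1, so 168 days after it is day 168 + 1 = 169. Days 162-169 (8 days) are included and days 170-176 (7 days) are excluded. A scan on its due date is included.

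**4. Who is exposed.** A patient first dosed d days before the last patient has 7 − d excluded window days. Exposure therefore ends at d = 6.

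**5. Expected loss.** Inputs from the documents: 6 patients enrolled by 25-Mar-2016 and 9 by 27-Jun-2016 (amendment log), so 3 patients in 94 days. Assumptions not in the documents: scan days uniform over the window, true ORR 30-50%, 10-30% of responders first responding at week 16, no other repeat scan, and the missing scan would have confirmed.

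- Last patient: 7/15 = 0.467.
- Neighbouring patients: (3/94) × (6 + 5 + 4 + 3 + 2 + 1)/15 = 0.0319 × 1.4 = 0.045.
- Total late-scan exposure: 0.511 patients.
- Low end: 0.511 × 0.30 × 0.10 = 0.015 responders.
- High end: 0.511 × 0.50 × 0.30 = 0.077 responders.

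That is about 0.02 to 0.08 responders. Divided by 20, it is about 0.08 to 0.38 percentage points of ORR. Faster accrual raises only the 0.045 term. The route through an unknown week-16 scan is additional and cannot be sized from the documents.

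**6. Effect on the operating characteristic at ORR 30%.** With one exposed patient and a loss probability of 0.5 (close to 7/15), 58.4% becomes 58.1% if the week-16 share is 10%, and 57.5% if it is 30%. The extreme bound, in which any response in that patient is certain to be lost, is 52.6%.

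**7. Effect at the boundary.** Losing one responder from 6/20 gives 5/20, with an exact 95% CI of 8.7-49.1%, which includes 10%.

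**The case against.** The strongest reply is that the cut-off is not a hard date. The SAP says *around* 168 days, leaves the date to be determined before database lock, and treats 6 cycles as a minimum, so a cut-off on day 176 already complies with both documents. This stands, and it removes any need to change the protocol. It does not remove the gap: nothing requires the date to wait for the scan, and the only stated reason for moving it is development or submission status. In an open-label study a date fixed by rule is also preferable to one chosen when individual responses are visible.

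Other replies also stand and limit the size:

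- In the earlier study of prior-ALK-inhibitor patients (Protocol 1.2.1.2.2) the median time to response was 6.1 weeks. Most responses should therefore be seen at week 8 and confirmed at week 16.
- Any repeat scan at least 4 weeks later can confirm, including an unscheduled one before the cut-off.
- The study stays open, so the final analysis picks up the missing scan.
- No hypothesis test is planned. The 10% rate describes the design and is not a formal decision rule.

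A reader might infer more than the documents support:

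- *That the scan's due day itself is lost, so that 8 of 15 days are excluded.* This requires reading the cut-off as study day 168. The SAP's day convention gives 169.
- *That the 24.1-week maximum time to response in the earlier study shows the problem.* A response first seen then could not be confirmed by day 176 either, because confirmation needs at least 4 more weeks.
- *That ORR is biased by 5 points.* That is the effect if a responder is actually lost. The expected effect is below half a point.

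**Conclusion.** The mismatch is real but narrow. It essentially concerns the last patient, with about 0.045 of a further patient's exposure at the logged accrual. It matters only if confirmation depends on the week-24 scan and that scan is taken late in its window. The expected loss of about 0.02 to 0.08 responders rests on the assumed week-16 share, the assumed ORR range and uniform scan timing.

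The loss can only lower ORR, it can be avoided, and it is confined to the primary (interim) CSR. Its practical importance lies at exactly 6 responders, where one patient decides whether the reported interval excludes 10%. This is a cheap improvement to the plan. It does not show that the primary analysis is invalid, and the documents do not support a claim that a response will be lost.

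**What to change.** In SAP 2.1 and 4.1, define the primary cut-off as the date when every patient still under tumor assessment has had the Cycle 7 Day 1 scan, or at the latest the date when the last patient's Cycle 7 Day 1 window closes (study day 176, i.e. 175 days after first dose).

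The cost is a SAP wording change and a delay of about 7 days. It adds no scans and no patients. The protocol can stay as it is, because its trigger is a minimum of 6 cycles. The change does not rescue responses first seen at week 24 in the latest patients; those still wait for the final analysis.

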2.2 Analysis sets

[figure not shown]
A patient is considered to be enrolled into the study if they have signed informed consent. Only patients who have signed informed consent will be included in the analysis sets.

Full Analysis Set

The Full Analysis Set (FAS) will include all patients who receive at least one dose of LDK378. The FAS will be used for summaries of baseline characteristics and all efficacy analyses, unless otherwise specified.

Safety Set

The Safety Set will include all patients who receive at least one dose of LDK378. All safety data will be analyzed using the Safety Set. In this non-randomized study the FAS and Safety Set are identical.

Frequency counts and percentages (using FAS as denominator) of patients in each of the above defined analysis sets will be summarized. In addition, a listing of patients included in each of the analysis sets will be provided.

[Section 4.2](#) provides further details regarding the derivation the analysis sets.

2.3 Patient demographics and other baseline characteristics

The FAS will be used for all patient demographic and baseline characteristic summaries and listings with the exception of screen failures.

CONFIDENTIAL - For Business Use Only

Basic demographic and background data

All demographic and baseline disease characteristics data will be summarized and listed. Categorical data (e.g. gender, age category; <65 and \geq 65 years, race, ethnicity, WHO performance status, smoking history) will be summarized by frequency count and percentages. Continuous data (e.g. age, weight, height, body mass index) will be summarized by descriptive statistics (as defined in [Section 2.1](#)).

Diagnosis and extent of cancer

Descriptive statistics and frequency counts and percentages will be tabulated, as appropriate, for diagnosis and extent of cancer based on the data collected on the electronic Case Report Form (eCRF) including diagnosis of disease, predominant histology/cytology, histological grade, time (in months) since initial diagnosis to start date of study drug, stage at initial diagnosis, stage at time of study entry, time (in months) from initial diagnosis to first recurrence/progression, time (in months) since most recent relapse/progression to start date of study drug, current extent of disease (metastatic sites), number of metastatic sites at baseline, types of lesions (target and non-target lesions) at baseline, number of target lesions at baseline, and disease burden at baseline for target lesion (based on the data collected on the RECIST eCRF page). A listing will also be provided including the information such as the ones above.

ALK status

ALK status at screening, collected on the [ALK Translocation status] eCRF page, will be listed.

Medical history

Medical history and current medical conditions will be summarized and listed. Separate summaries will be presented for medical history and current medical conditions. The summaries will be presented by primary system organ class and preferred term.

A medical condition that is not active at the study entry (i.e., 'Ongoing' is 'No' on the [Medical History] eCRF page) is classified as medical history (historical medical conditions). A medical condition that is active at the study entry (i.e., 'Ongoing' is 'Yes' on the [Medical History] eCRF page) is classified as current medical conditions. Medical history and current medical conditions are coded using the Medical Dictionary for Regulatory Activities (MedDRA) terminology.

Prior antineoplastic therapy

Prior antineoplastic (anticancer) therapy will be listed in three separate categories: (i) medications, (ii) radiotherapy, and (iii) surgery.

The number and percentage of patients who received any prior antineoplastic therapy (including medication, radiotherapy or surgery), prior antineoplastic medication, prior antineoplastic radiotherapy or prior antineoplastic surgery will be summarized.

All patients must have received alectinib for inclusion in the study; reason for alectinib discontinuation, best response on alectinib, duration of best response, and time from start of

last alectinib treatment to progression (date of progression on alectinib – start date of last alectinib treatment + 1) will be summarized. Prior crizotinib therapy will be summarized in a similar way to alectinib for patients previously treated with crizotinib.

Prior antineoplastic medications will be summarized by chemotherapy (medication) setting, other therapy (medication) setting, number of prior regimens, prior anticancer medications (including alectinib, crizotinib, cisplatin, carboplatin, pemetrexed, docetaxel, gemcitabine, bevacizumab, erlotinib, vinorelbine, gefitinib, paclitaxel, and others), therapy type at last treatment, and setting at last treatment. Prior antineoplastic medications will also be summarized by ATC class and preferred term.

Prior antineoplastic radiotherapy will be summarized by locations, setting at last radiotherapy, and time since end of last radiotherapy to start date of study drug (by category).

Prior antineoplastic surgery will be summarized by procedure at last surgery and time since last surgery to start date of study drug (by category).

Screen failures

Screen failures are patients who have been enrolled and have failed to meet inclusion and/or exclusion criteria. These patients are not treated with study drug. Frequency counts and percentages will be tabulated for all enrolled (screened) patients as follows:

- Number (%) of patients who completed screening phase (based on the presence of ‘Date of study phase completion’ and ‘Next phase entered’ is ‘Treatment’ (or ‘Will the subject continue into the next phase of the trial?’ is ‘Yes’) on the [End of Screening Phase Disposition] eCRF page);
- Number (%) of patients who discontinued during screening phase (based on the presence of ‘Date of discontinuation’, ‘Subject status (i.e., reason for discontinuation)’ entered, and ‘Will the subject continue into the next phase of the trial?’ is ‘No’ on the [End of Screening Phase Disposition] eCRF page);
 - Primary reasons for screening phase discontinuation (based on the ‘Subject status (i.e., reason for discontinuation)’ recorded on the [End of Screening Phase Disposition] eCRF page for patients who discontinued during screening phase).

All screen failures (i.e., patients who discontinued during screening phase) will be listed along with the relevant information such as reason(s) for screening phase discontinuation and the inclusion/exclusion criteria leading to screen failure. The eCRF data reported in screen failures will not be included in any data analyses, but it will be presented in separate listings as needed.

